Appendix 5. Definition of severe sepsis: at least 2 criteria A and one criteria B

Criteria A	-Cardiac pulse > 90/mn
	-Respiratory frequency > 20/mn
	-Mechanical ventilation
	-Temperature > 38°C or < 36°C
Criteria B	-Systolic blood pressure < 90 mmHg
	-Diuresis < 30 ml/h ou < 700 ml/24h
	-PaO2 < 75 mmHg or PaO2/FiO2 < 250
	-Encephalopathy (Glasgow score < 14)
	-Metabolic acidosis
	-Coagulopathy

Appendix 6. Acute GVHD

GVHD Grading and Staging Extent of Organ Involvement

State	Skin	Liver	Gut
1	rash on <25% of skin ^a	Bilirubin 2-3 Mg/dl ^b	Diarrhea >500 ml/day ^c or persistent nausea ^d
2	Rash on 25-50% of skin	Bilirubin 3-6 mg/dl	Diarrhea <1000 ml/day
3	Rash on >50% of skin	Bilirubin 6-15 mg/dl	Diarrhea >1500 ml/day
4	Generalized erythroderma with bullous formation	Bilirubin >15 mg/dl	Severe Abdominal pain with or without ileus
Grade			
1	Stage 1-2	None	None
	Stage 3 or	Stage 1 or	Stage 1
III		Stage 2-3 or	Stages 2-4
IVf	Stage 4	Stage 4	

a = Use "rule of Nines" or burn chart to determine extent of rash.

^b = Range given as total bilirubin. Downgrade one stage if an additional cause of elevated bilirubin has been documented.

- c = Volume of diarrhea applies to adults. for pediatric patients, the volume of diarrhea should be based on body surface area. Downgrade one stage if an additional cause of diarrhea has been documented.
- ^d = Persistent nausea with histologic evidence of GVHD in the stomach of duodenum.
- e = Criteria for grading given as minimum degree of organ involvvement required to confer that grade.
- f = Grade IV may also include lesser organ involvement with an extreme decrease in performance status.

Ap09 1.ppt

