- ✓ Risk factors for overall survival and non-relapse mortality after the transplant including iron overload (SF, Non Transferrin Binding Iron)
- ✓ For transplanted patients only: cumulative incidence of neutrophil engraftment on day 60 posttransplant, acute and chronic GVHD at 2 years post-transplant

4. Patient Selection

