According to national and European guidelines, all patients will received a prophylaxis for herpes simplex (acyclovir or valacyclovir), pneumocystis and toxoplamosis (sulfametoxazole/trimethoprime or sulfadoxine/pyrimethamine or atovaquone) except during aplasia, anti-fungal therapy (fluconazole).

All patients will be monitored for CMV and EBV reactivation by weekly PCR in blood until the third month.

No engraftment

If the patient has acute or late rejection with persistent of severe pancytopenia, a second transplant has to be discussed. The quicker this second transplant is performed, the best chance the patient has to avoid severe infection. According to performance status and comorbidities, a second transplant with same or different donor can be re-scheduled as soon as possible, if possible no later than 3 weeks after rejection diagnosis.

If the patient has an autologous reconstitution with good or moderate hematological reconstitution, or returns to his baseline count, a second allogeneic transplant is not recommended until the disease progresses.

Management of immunosuppressive treatment and donor lymphocyte infusion

As reported in the regimen schema, Mycophenolate Mofetil will be decreased from day 30 and stop on day 45 while Cyclosporine will be decreased on day 120, 25% per 2 weeks in absence of acute GVHD. The optimal dosage of Cyclosporine between D0 and D120 will be between 150 and 350 ng/ml when intravenous and a residual > 150 ng/ml (< 350) when oral route.

There is no systematical preventive donor lymphocyte infusion in this trial (because patients are at low risk).

In some cases, immunosuppressive therapy can continued later if the patient presents acute GVHD until acute GVHD has resolved.

In other cases, if there are some evidences of disease activity and / or mixed chimerism after day 30, immunosuppressive treatment will be discontinued earlier (except if active GVHD). Patients should be evaluated 6 weeks after immunosuppressive discontinuation and in cases of persistence mixed chimerism and/or disease activity proven by marrow analysis, DLI should be planned (at least 6 weeks after immunosuppressive discontinuation) except if the patient had a previous grade II to IV acute GVHD or in patients with active chronic GVHD. The donor can be collected to have a set of 4 donor lymphocytes packages which can be infused in the recipient as follow:

-first: 1x10⁶ CD3+ cells /kg

-second: 0.5x10⁷ CD3+ cells /kg

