8.2. Visits

For all enrolled patients, visits will be performed:

- at inclusion
- every two weeks during the first 4 weeks (first month)
- every 4 weeks from the 5th week to the 26th week (until 6th month)
- every 8 weeks from the 27th week to the 52th week (until 12th month)
- every 12 weeks from the 53th week to the end of study.

At each patient visit, the following information will be registered:

- Grade III to IV adverse events (classified according to NCI- CTCAE 4.0) http://evs.nci.nih.gov/ftp1/CTCAE/CTCAE_4.03_2010-06-14_QuickReference_5x7.pdf

- Treatment by Exjade[®] and its dose
- Clinical assessment (every 2 weeks on first month)
- Weight, PS, serious infectious disease (defined in Appendix 4)
- Transfusion history (platelet and RBC) including the research of allo-immunisation (RAI)
- AST, ALT, serum bilirubin, serum creatinine, PAL, LDH, GGT, CRP

- Proteinuria (rapid urine test)

- Pregnancy test, if applicable
- Blood cell count including reticulocytes (every week during the 1th month then every 4 weeks)
- Ferritin level, transferrin level and saturation, plasmatic iron level
- In case of disease progression/relapse suspicion, marrow + cytogenetic analysis

Specific information for specific point (after inclusion):

- Quality of life questionnaire (EORTC) at 12, 24 and 36 months

- Centralized biological study (hepcidine, LPI, NTBI): At 3 and 16 months after inclusion (specific form in Appendix 10)

- **Bone marrow aspiration** with cytogenetic (local laboratories) and molecular biology (CHRU Lille) will be performed according to local policy but at least once a year

For patients who received a transplant:

- Pre-graft tests including cardiac assessment and respiratory assessment with pulmonary tests

- **Centralized biological study (hepcidine, LPI, NTBI):** just before conditioning regimen (D-5), just before transplant on day 0, and on day 7, 30, 100, 365 post-transplant

- Between 2 to 3 months after the transplant, a **bone marrow aspiration** (with shipment for biological study: BM 2 ml EDTA)

- At least one post-transplant **chimerism** in blood after engraftment on day 30. The chimerism will be repeated only if the first one is not donor > 95% or in cases a rejection is suspected

- Acute GVHD grade per organ at each visit (Appendix 6)

- Neutrophil engraftment and platelet engraftment (within 60 days post-transplant)

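### Appendix 6 prints gut stage 2 of the acute GVHD scale as an upper bound between two lower bounds, so the gut scale is not ordered and literal use could misgrade severity

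*Protocol*

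**What the plan says.** Protocol Appendix 6 stages acute GVHD separately for skin, liver and gut, then converts the stages to an overall grade. The diarrhea criteria in the gut column are:

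- stage 1: "Diarrhea >500 ml/day", or persistent nausea;
- stage 2: "Diarrhea <1000 ml/day";
- stage 3: "Diarrhea >1500 ml/day".

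Stage 4 is defined by severe abdominal pain, not by volume. In the grade rows, gut stages 2 to 4 belong to grade III. Gut stage 1 sits in the row between grades 1 and III. The label of that row is missing from the text as read from the PDF, and it is taken here as grade II. A footnote says how the rows work: "Criteria for grading given as minimum degree of organ involvvement required to confer that grade".

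Three places in the protocol depend on acute GVHD or its grade:

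- Section 8.2 (Visits) requires the grade per organ at each visit and refers to Appendix 6.
- Section 3.2 lists, for transplanted patients, the cumulative incidence of "acute and chronic GVHD at 2 years post-transplant".
- Section 6.1 plans DLI in defined circumstances, "except if the patient had a previous grade II to IV acute GVHD".

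**The concern.** Severity stages should rise with severity. The skin stages do, by extent of rash. The liver stages do as well, with stage 2 at "Bilirubin 3-6 mg/dl" between a lower and a higher bilirubin range. In the gut column, stages 1 and 3 are lower bounds and stage 2 alone is an upper bound. A smaller stool volume can therefore earn a higher stage than a larger one.

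The boundary between gut stages 1 and 2 is also the gut boundary between overall grades II and III, so the slip carries into the grade. Because the protocol offers no other acute GVHD scale, a site that follows the table and a site that silently corrects it could grade the same patient differently. The study plans 20 to 25 centers.

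**Working it through.** No sample size or power figure is involved. The check applies the printed criteria to every range of stool volume.

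**Inputs** (all Appendix 6): stage 1 if volume > 500; stage 2 if volume < 1000; stage 3 if volume > 1500 ml/day. Gut stage 1 gives grade II (label inferred from row order) and gut stages 2-4 give grade III. Only gut involvement is considered, without persistent nausea. Where two stages are met, the higher is taken; this is an assumption, since the appendix does not say.

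**Step 1: the rows as printed**

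| Diarrhea, ml/day | > 500? | < 1000? | > 1500? | Stages met | Grade from highest stage |
|---|---|---|---|---|---|
| up to 500 | no | yes | no | 2 | III |
| 501-999 | yes | yes | no | 1 and 2 | III (II if stage 1 is chosen) |
| 1000-1500 | yes | no | no | 1 | II |
| above 1500 | yes | no | yes | 1 and 3 | III |

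A patient with 300 ml/day is stage 2, grade III; a patient with 1200 ml/day is stage 1, grade II. The order is reversed.

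**Step 2: can another reading that keeps the printed sign rescue the scale?**

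- Read stage 2 as more than 500 and less than 1000. It then coincides with part of stage 1, and 1000-1500 still gets only stage 1, below the stage available to 501-999.
- Take the lowest stage met instead of the highest. Volumes up to 500 are still stage 2, while 1600 ml/day becomes stage 1.

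Neither gives an ordered scale.

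**Step 3: the rows with stage 2 as a lower bound at the same 1000**

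| Diarrhea, ml/day | Highest stage | Grade | Printed rows gave |
|---|---|---|---|
| up to 500 | none from volume | none from gut | III |
| 501-999 | 1 | II | III, or II if stage 1 is chosen |
| 1000 | 1 | II | II |
| 1001-1500 | 2 | III | II |
| above 1500 | 3 | III | III |

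The scale is now monotone. This shows that the sign of one row accounts for the whole disorder.

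**Step 4: which differences cross the grade II to IV line in Section 6.1?** A change between II and III stays inside the category. Only volumes up to 500 ml/day move from no gut grade to grade III, and so enter it.

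**The case against.** The evidence is one character in a table that the PDF reading has damaged: a grade label is missing and some other characters are garbled. A misread sign cannot be excluded without the original page. This stands, and it is why the fix begins with that check.

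Experienced transplant centers may also see the intended direction from the neighboring rows and from the skin and liver columns, and ignore the slip. That is plausible. Nothing in the protocol shows that any patient has been misgraded, so the point holds only for literal use. It does not remove the risk that some sites follow the table and others do not.

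Three stronger readings are tempting, and the document does not support them:

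- **That the DLI rule is affected generally.** Section 6.1 treats grades II to IV together, so a swap between II and III changes nothing there. Only gut-only cases at or below 500 ml/day, without qualifying nausea and without skin or liver involvement that already reaches grade II, would cross the line.
- **That the acute GVHD endpoint is distorted throughout.** Section 3.2 states no grade cut-off for the cumulative incidence. A swap between II and III does not alter whether acute GVHD occurred; only the band up to 500 ml/day could.
- **That some 50 to 59 patients are affected.** The 62 group A patients (Section 5) and the expected 80 to 95% transplanted (Section 3.2) give 62 × 0.80 = 49.6 and 62 × 0.95 = 58.9. That is the number expected to be assessed on the scale. The protocol gives no rate of gut GVHD, so the number misgraded cannot be derived.

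**Conclusion.** The concern holds in a limited form. As printed, the gut column of Appendix 6 is not an ordered scale, no reading that keeps the sign makes it one, and nothing elsewhere in the protocol corrects it. It is the operative scale for each visit, so this is more than a slip in background text.

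If the row is applied literally, every volume from above zero to 1500 ml/day, apart from exactly 1000, is either ambiguous or graded differently from a scale with stage 2 as a lower bound at 1000. Volumes above 1500 ml/day, stage 4, persistent nausea, and skin and liver staging do not depend on the row.

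The consequences are confined to the recorded severity of acute GVHD in transplanted patients, its consistency between sites, and a narrow set of cases under the DLI exception. The primary comparison of overall survival and the sample size are unaffected. The conclusion rests on two assumptions to be verified on the original page: that the sign is printed as read, and that the unlabeled grade row is grade II.

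**What to change.** Check the sign of gut stage 2, and the label of the grade row that contains gut stage 1, on the original page of Appendix 6. If the sign is confirmed, reconcile the three gut rows with each other so that the stages are ordered and do not overlap. A lower bound at the printed 1000 ml/day would restore order using the table's own numbers; the sponsor should confirm which criterion was intended.

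Then make the electronic CRF match the reconciled rows. It is not part of the protocol, so whether it carries the same sign is unknown. For patients already graded with gut involvement, query the gut stage where source data allow. The protocol asks for the grade per organ and does not say that stool volume is collected, so some cases may not be recoverable.

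The cost is a one-character correction to an appendix, a CRF check and a small targeted query.

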Appendix 7. Chronic GVHD

	SCORE 0	SCORE 1	SCORE 2	SCORE 3
PERFORMANCE SCORE:	Asymptomatic and fully active (ECOG 0; KPS or LPS 100%)	Symptomatic, fully ambulatory, restricted only in physically strenuous activity (ECOG 1, KPS or LPS 80-90%)	Symptomatic, ambulatory, capable of self-care, >50% of waking hours out of bed (ECOG 2, KPS or LPS 60-70%)	Symptomatic, limited self-care, >50% of waking hours in bed (ECOG 3-4, KPS or LPS <60%)
SKIN Clinical features: Maculopapular rash Lichen planus-like features Papulosquamous lesions or icthyosis Hyperpigmentation Hypopigmentation Keratosis pilaris Erythema Erythroderma Polikiloderma Sclerotic features Pruritus Hair involvement Nail involvement % BSA involved	No Symptoms	<18% BSA with disease signs but NO sclerotic features	19-50% BSA OR involvement with superficial sclerotic features "not hidebound" (able to pinch)	>50% BSA OR deep sclerotic features "hidebound" (unable to pinch) OR impaired mobility, ulceration or severe pruritus
Моитн	No symptoms	Mild symptoms with disease signs but not limiting oral intake significantly	Moderate symptoms with signs with partial limitation of oral intake	Severe symptoms with disease signs on examination with major limitation of oral intake
EYES Mean tear test (mm): >10 6-10 <5 Not done	No symptoms	Mild dry eye symptoms not affecting ADL (requiring eyedrops ≤ 3 x per day) OR asymptomatic signs of keratoconjunctivitis sicca	Moderate dry eye symptoms partially affecting ADL (requiring drops > 3 x per day or punctal plugs), WITHOUT vision impairment	Severe dry eye symptoms significantly affecting ADL (special eyeware to relieve pain) OR unable to work because ocular symptoms OR loss of vision caused by keratoconjunctivitis sicca

GI TRACT	No symptoms	Symptoms such as dysphagia, anorexia, nausea, vomiting, abdominal pain or diarrhea without significant weight loss (<5%)	Symptoms associated with mild to moderate weight loss (5-15%)	Symptoms associated with significant weight loss >15%, requires nutritional supplement for most calorie needs OR esophageal dilation
LIVER * AP may be elevate	Normal LFT ed in growing children, and	Elevated Bilirubin, AP*, AST or ALT <2 x ULN d not reflective of liver dy	Bilirubin >3 mg/dl or Bilirubin, enzymes 2-5 x ULN ysfunction	Bilirubin or enzymes > 5 x ULN
,	SCORE 0	SCORE 1	SCORE 2	SCORE 3
	No symptoms	Mild symptoms (dyspnea with stair climbing)	Moderate symptoms (dyspnea with level walking)	Severe symptoms (dyspnea at rest; requiring 0 ₂)
DLCO	FEV1 > 80% OR LFS=2	FEV1 60-79% OR LFS 3-5	FEV1 40-59% OR LFS 6-9	FEV1 ≤ 39% OR LFS 9-12
Joints and Fascia	No symptoms	Mild tightness of arms or legs, normal or mild decreased range of motion (ROM) AND not affecting ADL	Tightness of arms or legs OR joint contractures, erythema thought due to fasciitis, moderate decrease ROM AND mild to moderate limitation of ADL	Contractures WITH significant decrease of ROM AND significant limitation of ADL (unable to tie shoes, button shirts, dress self etc.)
GENITAL TRACT	No symptoms	Symptomatic with mild signs on exam AND no effect on coitus and minimal discomfort with gynecologic exam	Symptomatic with moderate signs on exam AND with mild dyspareunia or discomfort with gynecologic exam	Symptomatic WITH advanced signs (stricture, labialagglutination or severe ulceration) AND severe pain with coitus or inability to insert vaginal speculum

Other indicators, clinical manifestations or complications related to chronic GVHD (check all that apply and assign a score to its severity (0-3) based on its functional impact where applicable (none – 0,mild -1, moderate -2, severe – 3)

اً Esophageal stricture or w	eb ¹ Pericardial Effusion	^آ Pleural Effusion(s)
آ Ascites (serositis)	راً Nephrotic syndrome	¹ Peripheral Neuropathy
رًا Myasthenia Gravis	ر Cardiomyopathy	¹ Eosinophilia > 500μl
اً Polymyositis	رًا Cardiac conduction defects	Coronary artery involvement

¹ Platelets <100,000/μl ____ ¹ Progressive onset___

1́Отнекs: Specify:_____

Pulmonary scoring should be performed using both the symptom and pulmonary function testing (PFT) scale whenever possible. Scoring using the Lung Function Score (LFS) is preferred, but if DLCO is not available, grading using FEV1 should be used. The LFS is a global assessment of lung function after the diagnosis of bronchiolitis obliterans has already been established. The percent predicted FEV1 and DLCO (adjusted for hematocrit but not alveolar volume) should be converted to a numeric score as follows: > 80% = 1; 70-79% = 2; 60-69% = 3; 50-59% = 4; 40-49% = 5; < 40% = 6. The LFS = FEV1 score + DLCO score, with a possible range of 2-12.

Abbreviations: GVHD (graft versus host disease); ECOG (Eastern Cooperative Oncology Group), KPS (Karnofsky Performance Status), LPS (Lansky Performance Status); BSA (body surface area); ADL (activities of daily living); LFTs (liver function tests); AP (alkaline phosphatase); ALT (alanine aminotransferase); AST (aspartate aminotransferase); ULN (upper limit of normal)

Mild chronic GVHD involves only 1 or 2 organs or sites (except lung: see below) with no clinically significant functional impairment (maximum of score 1 in all affected organs or sites).

Moderate chronic GVHD involves i) at least one organ or site with clinically significant but no major disability (maximum of score 2 in any affected organ or site), or ii) three or more organs or sites with no clinically significant functional impairment (maximum score of 1 in all affected organs or sites). A lung score of 1 will also be considered moderate chronic GVHD.

Severe chronic GVHD indicates major disability caused by chronic GVHD (score of 3 in any organ or site). A lung score of 2 or greater will also be considered severe chronic GVHD

Appendix 8. IWG 2006 response criteria

Modified International Working Group response criteria for altering natural history of MDS

EVALUATION OF RESPONSE FOR MDS

In order to apply, responses must last at least 4 weeks.

1. Complete remission

Bone marrow: less than 5% myeloblasts with normal maturation of all cell lines. Persistent dysplasia will be noted*† Peripheral blood: Hgb \geq 11 g/dL Platelets \geq 100 x 10⁹/L Neutrophils \geq 1.0 x 10⁹/L Blasts 0%

2. Partial remission

All CR criteria if abnormal before treatment except: Bone marrow blasts decreased by at least 50% over pretreatment but still more than 5% Cellularity and morphology not relevant

3. Marrow CR

Bone marrow: maximum of 5% myeloblasts and decrease by at least 50% over pretreatment Peripheral blood: if HI responses, they will be noted in addition to marrow CR

4. Stable disease

Failure to achieve at least PR, but no evidence of progression for at least 8 wks

5. Failure

Death during treatment or disease progression characterized by worsening of cytopenias, increase in percentage of bone marrow blasts, or progression to a more advanced MDS FAB subtype than pre-treatment.

6. Relapse after CR or PR

At least 1 of the following:

Return to pretreatment bone marrow blast percentage

Decrement of at least 50% from maximum remission/response levels in granulocytes or platelets Reduction in Hgb concentration by at least 1.5 g/dL or transfusion dependence

7. Cytogenetic response

Complete

Disappearance of the chromosomal abnormality without appearance of new ones

Partial

At least 50% reduction of the chromosomal abnormality

8. Disease progression

For patients with: Less than 5% blasts: at least 50% increase in blasts to more than 5% blasts 5%-10% blasts: at least 50% increase to more than 10% blasts 10%-20% blasts: at least 50% increase to more than 20% blasts 20%-30% blasts: at least 50% increase to more than 30% blasts Any of the following: At least 50% decrement from maximum remission/response in granulocytes or platelets Reduction in Hgb by at least 2 g/dL Transfusion dependence

9. Survival

Endpoints: Overall: death from any cause Event free: failure or death from any cause PFS: disease progression or death from MDS DFS: time to relapse Cause-specific death: death related to MDS

Modified criteria of the IWG 2006 for hematologic improvement In order to apply, responses must last at least 8 weeks.

Erythroid response (pretreatment < 11 g/dL)

Hgb increase at least by 1.5 g/dL

Relevant reduction of units of RBC transfusions by an absolute number of at least 4 RBC transfusions / 8 wk compared with the pretreatment transfusion number in the previous 8 wk. Only RBC transfusions given for a Hgb of below or equal to 9.0 g/dL pretreatment will count in the RBC transfusion response evaluation

Platelet response (pretreatment 100 x 10⁹/L)

Absolute increase of at least 30×10^9 /L for patients starting with more than 20×10^9 /L platelets Increase from less than 20×10^9 /L to more than 20×10^9 /L and by at least 100%

Neutrophil response (pretreatment < 1.0 x 10⁹/L)

At least 100% increase and an absolute increase of at least 0.5x10⁹/L

Progression or relapse after HI

At least 1 of the following: At least 50% decrement from maximum response levels in granulocytes or platelets Reduction in Hgb by at least 1.5 g/dL Transfusion dependence

Appendix 9. CTCAE V4

TOXICITY CRITERIA (CTCAE)

Cancer Therapy Evaluation Program

http://evs.nci.nih.gov/ftp1/CTCAE/CTCAE_4.03_2010-06-14_QuickReference_5x7.pdf

Appendix 10. Centralized biological study (Hepcidine, NTBI, LPI)

2 blood Serum	tube (tube sec, 5ml)								
To be sent from Mo	onday to wednesday to:								
[name]									
Service de Biochimie / Centre Français des Porphyries									
Hôpital Louis Mourier [name], France [contact] [contact]									
									n samples: day or -80°C for sample sent afterward)
FOR NON TRANSPLANT PATIENT FOR TRANSPLANT PATIENT									
	FOR TRANSPLANT PATIENT								
At Screening	FOR TRANSPLANT PATIENT At Screening								
At Screening									
	At Screening								
At Screening At M3 Post-Inclusion	At Screening At D-5 Pre-Transplant								
At Screening At M3 Post-Inclusion	At Screening At D-5 Pre-Transplant At D0 Pre-Transplant								
At Screening At M3 Post-Inclusion	At Screening At D-5 Pre-Transplant At D0 Pre-Transplant At D7 Post-Transplant								

